2.2.7 Clinical Efficacy

Study MT103-104- Study Design and Population

Study MT103-104 was an open-label, dose-escalation, multicenter, phase 1 study in Germany to investigate the tolerability and safety of blinatumomab given as cIV infusion over 4 or 8 weeks in adult patients with relapsed NHL. This study has been completed. Blinatumomab was administered to 76 patients. The distribution of histologic subtypes in the study population was FL in 37%, other subtypes of indolent lymphoma in 13%, MCL in 32%, and DLBCL in 18%. Among treated patients, the median number of prior treatment regimens was 3, the average age was 60 years (range 20-80 years), and the majority of patients (75%) were men.

In Study MT103-104, the antitumor activity of blinatumomab in terms of objective response was assessed using Cheson criteria(11), and all CT scans were centrally reviewed by an independent radiologist. Table 2-6 shows the response rates at different dose levels in Study MT103-104. The efficacy of blinatumomab was dose-dependent, with objective responses starting at a blinatumomab dose of 15 $\mu\text{g}/\text{m}^2/\text{day}$. At a dose of 5 $\mu\text{g}/\text{m}^2/\text{day}$, biological activity in terms of compete depletion of peripheral B cells was observed. Three responses (2 partial responses [PRs], 1 CR) were observed in 15 patients treated with blinatumomab maximal 15 $\mu\text{g}/\text{m}^2/\text{day}$. In patients receiving blinatumomab maximal 60 $\mu\text{g}/\text{m}^2/\text{day}$ (either reached by step-wise dose escalation or by directly starting at this dose), a 69% objective response rate (24/35 patients: CR/unconfirmed CR [CRu] in 13 patients and PR in 11 patients) was observed. The mean duration of response was 15.4 months (95% confidence interval = 6.8, 37.1) (transplant not counted as progression). At blinatumomab maximal 90 $\mu\text{g}/\text{m}^2/\text{day}$, 1 of the 4 patients showed a CR and 1 showed a PR. One of the 4 patients could not be evaluated due to early treatment discontinuations due to dose-limiting toxicity (DLT) (2 DLTs of encephalopathy).

Table 2-6. Responses by Maximal Dose Received in Study MT103-104 for All NHL Entities

Blinatumomab Dose Level ^a	Patients (N=76)	Complete Response ^b	Partial Response	Total Responses ^c	Overall Response Rate
<5 $\mu\text{g}/\text{m}^2/\text{day}$	9	0	0	0/9	0.0%
5 $\mu\text{g}/\text{m}^2/\text{day}$	7	0	0	0/7	0%
15 $\mu\text{g}/\text{m}^2/\text{day}$	15	1	2	3/15	20.0%
30 $\mu\text{g}/\text{m}^2/\text{day}$	6	1	0	1/5	20.0%
60 $\mu\text{g}/\text{m}^2/\text{day}$	35	8	11	24/35	69.0%
90 $\mu\text{g}/\text{m}^2/\text{day}$	4	1	1	2/4	50.0%

^a Dose level based on maximal dose reached.

^b Includes CRu (unconfirmed complete response).

^c Complete response + partial response. Only includes patients who reached the highest target dose.

2.3 Rationale

Indolent B-cell lymphomas remain incurable diseases in the modern era. Despite numerous available therapies, subjects typically display a pattern of ongoing relapse during their lives, and additional therapies are still needed, particularly those that are not chemotherapy-based.

Blinatumomab is a bispecific antibody targeting CD19 and CD3 with activity in B cell acute lymphoblastic leukemia and NHL. In a phase I study including indolent NHL, 8 of 9 subjects treated at a constant dose exceeding 60ug/m2/d had an objective response with a median duration of response of 26 months. (12) Treatment was well tolerated with the most common AEs being transient/reversible fever, headache and fatigue. Out of 52 subjects, 9 discontinued treatment due to CNS toxicity including kinetic tremor, speech impairment, disorientation, apraxia and seizure which resolved upon stopping study drug. A baseline B cell to T cell (B:T) ratio in peripheral blood at or below 1:10 has been identified as a predictive factor for occurrence of neurological AEs.(13) Neurologic events were reversible. Given the significant signal of activity of blinatumomab in indolent B-cell NHL and the overall favorable safety profile, we propose a phase 2 study of blinatumomab in relapsed/refractory indolent NHL.

2.4 Correlative Studies Background

2.4.1 Neurologic toxicity

Patients receiving blinatumomab may experience a spectrum of neurologic events, the most clinically relevant being encephalopathy, confusional and cognitive disorders, memory impairment, disorientation, convulsions (convulsion, grand mal seizure, and epilepsy), speech disorders (aphasia, speech disorder, and dysarthria), cerebellar syndrome, tremor, and hallucinations. Across all indications/studies, the incidence of patients experiencing neurologic events is greatest within the first few days of blinatumomab treatment. Most of these events are clinically manageable after interruption or permanent discontinuation of blinatumomab. Of the 477 subjects enrolled across the program as of 10 October 2013, 243 patients (51%) have experienced neurologic TEAEs, and 197 (41%) were considered by the investigator as related to treatment. The majority of TEAEs occurred within the first week of the first cycle of blinatumomab treatment. Overall, the types of events observed in the R/R ALL population were similar to those in the MRD-positive and R/R NHL populations, with no major differences in the frequencies of events between indications. Serious neurologic events were observed at blinatumomab doses ranging from 5 to 90 μ g/m2/day, with higher doses (60 and 90 μ g/m2/day) associated with an increased severity of events in the NHL studies. Prodromal symptoms included tremor and disorientation. No specific pattern was observed in medical histories or concomitant medications. A baseline B cell to T cell (B:T) ratio in peripheral blood at or below 1:10 has been identified as a predictive factor for occurrence of neurological AEs.(13) We will correlate baseline B cell to T cell (B:T) ratio in peripheral blood measured by flow cytometry with neurologic events in a descriptive manner.

3. PARTICIPANT SELECTION

3.1 Eligibility Criteria

3.1.1 Subjects must have histologically determined B cell NHL that is relapsed or primary refractory after initial therapy.

- Follicular Lymphoma of any grade
- Marginal zone lymphoma (extranodal, nodal, or splenic). Patients with gastric MALT must have progressed after H. Pylori therapy and radiation. Patients with splenic MZL must have prior splenectomy.

3.1.2 At least 1 prior line of chemoimmunotherapy if primary refractory or relapsed with in one year. Subjects who respond to initial therapy for greater than one year must have had at least 2 prior lines of therapy including one line with chemoimmunotherapy including an anti-CD20 monoclonal antibody

3.1.3 Measurable disease that has not been previously irradiated on PET-CT of at least 1.5cm,

3.1.4 Age ≥ 18 years.

3.1.5 ECOG performance status ≤ 2 (see Appendix A)

3.1.6 Participants must have adequate organ and marrow function as defined below:

– absolute neutrophil count	$\geq 750/\text{mcL}$
– platelets	$\geq 75,000/\text{mcL}$
– total bilirubin	$< 2.0 \times$ upper limit of normal (ULN)
– AST(SGOT)/ALT(SGPT)	$\leq 2.5 \times$ institutional upper limit of normal or $\leq 5 \times$ ULN – if due to lymphoma infiltration
– creatinine	$\leq 2.0 \times$ ULN

OR

– creatinine clearance	$\geq 50 \text{ mL/min}/1.73 \text{ m}^2$ for participants with creatinine levels above $2.0 \times$ ULN .
------------------------	--

3.1.7 Ability to understand and the willingness to sign a written informed consent document.

3.2 Exclusion Criteria

- 3.2.1 Participants who have had chemotherapy within 3 weeks, rituximab or obinutuzumab within 4 weeks, or radioimmunotherapy within 6 weeks prior to entering the study, or those who have not recovered from adverse events due to agents administered more than 3 weeks earlier. Subjects actively progressing within that window who have recovered from toxicities of prior therapy are also eligible.
- 3.2.2 Autologous stem cell transplantation within 12 weeks prior to study entry
- 3.2.3 Prior allogeneic transplant
- 3.2.4 Therapeutic doses of corticosteroids within 14 days prior to study entry, defined as >20mg/day pf prednisone, or equivalent. Topical and/or inhaled steroids are permitted.
- 3.2.5 Participants who are receiving any other investigational agents.
- 3.2.6 Participants with known brain metastases should be excluded from this clinical trial because of their poor prognosis and because they often develop progressive neurologic dysfunction that would confound the evaluation of neurologic and other adverse events.
- 3.2.7 History of allergic reactions attributed to compounds of similar chemical or biologic composition to blinatumomab
- 3.2.8 Subjects with known HIV infection
- 3.2.9 Pregnant or lactating subjects.
- 3.2.10 Chronic infection with hepatitis B or hepatitis C virus
- 3.2.11 History of or current relevant CNS pathology such as epilepsy, seizure, paresis, aphasia, apoplexia, severe brain injuries, cerebellar disease, organic brain syndrome, psychosis
- 3.2.12 Prior history of another malignancy (except for non-melanoma skin cancer, *in situ* cervical or breast cancer, or localized prostate cancer) unless disease free for at least one year and felt at low risk of relapse by treating physician.
- 3.2.13 Uncontrolled intercurrent illness including, but not limited to, ongoing or uncontrolled systemic fungal, bacterial, viral, or other infection, symptomatic congestive heart failure, unstable angina pectoris, cardiac arrhythmia, or psychiatric illness/social situations that would limit compliance with study requirements.

3.3 Inclusion of Women and Minorities

Both men and women of all races and ethnic groups are eligible for this trial

4. REGISTRATION PROCEDURES

4.1 General Guidelines for DF/HCC Institutions

Institutions will register eligible participants in the Clinical Trials Management System (CTMS) OnCore. Registrations must occur prior to the initiation of protocol therapy. Any participant not registered to the protocol before protocol therapy begins will be considered ineligible and registration will be denied.

An investigator will confirm eligibility criteria and a member of the study team will complete the protocol-specific eligibility checklist.

Following registration, participants may begin protocol therapy. Issues that would cause treatment delays should be discussed with the Overall Principal Investigator (PI). If a participant does not receive protocol therapy following registration, the participant's registration on the study must be canceled. Registration cancellations must be made in OnCore as soon as possible.

4.2 Registration Process for DF/HCC Institutions

DF/HCC Standard Operating Procedure for Human Subject Research Titled *Subject Protocol Registration* (SOP #: REGIST-101) must be followed.

4.3 General Guidelines for Other Investigative Sites

N/A

4.4 Registration Process for Other Investigative Sites

N/A

5. TREATMENT PLAN

5.1 Treatment Regimen

This will be an open label single arm phase II study employing a Simon's optimal two stage design to assess efficacy and safety of blinatumomab in indolent NHL. Blinatumomab will be administered as a continuous IV infusion through a central venous catheter for a 42 day cycle. Blinatumomab will start with a 7 day infusion at 9mcg/d. If no dose limiting toxicity (table 6.1)

after 7 days, the dose will be escalated to 28 mcg/d for 7 additional days. If no dose limiting toxicity (table 6.1) after 14 days, blinatumomab will be infused at a target dose of at 112mcg/d for 28 days. The first 5 patients enrolled on study will be admitted for 3 days during each dose escalation as well as the first 3 days of cycle 2 to monitor for cytokine release syndrome as well as neurotoxicity. If no grade 4 toxicities are seen, future patients enrolled on study will begin therapy as an outpatient. Subjects will be restaged after a 6 week treatment free period by PET CT. All subjects without disease progression will receive an additional 4 week cycle starting at the target dose of 112 mcg/d. All subjects will then have an end of treatment PET CT 6 weeks after completion of the second infusion. All subjects with a response will then be followed with a CT every 6 months for the first 2 years and then annually for 5 years or until progression.

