1. OBJECTIVES

1.1 Study Design

This will be an open label single arm phase II study employing a Simon's optimal two stage design to assess efficacy and safety of blinatumomab in indolent NHL. Blinatumomab will be administered as a continuous IV infusion with stepwise dosing reaching a target dose of at 112mcg/d for 28 days. Subjects will start at a dose of 9 mcg/d with escalation to 28mcg/d and 112mcg/d if no toxicity at 7 day intervals. Subjects will be restaged 6 weeks after completion of the infusion by PET CT. All subjects without disease progression will receive an additional 4 week cycle. All subjects will then have an end of treatment PET CT 6 weeks after completion of the second infusion. All subjects with a response will then be followed with a CT every 6 months for 2 years then annually through 5 years or until progression.

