2.2.5 Rationale of Clinical Dose Selection

Since there was no clinically meaningful effect of body size on blinatumomab clearance in adults (Figure 2-1), a fixed dosing regimen (ie, starting at $9 \mu\text{g}/\text{day}$ in week 1 followed by $28 \mu\text{g}/\text{day}$ in remaining weeks) was applied to the treatment of R/R ALL in adults. The BSA based dosing regimen was found to be appropriate in pediatric patients. Five dose schemes (5 , 15 , 30 , $15-30$ and $5-15 \mu\text{g}/\text{m}^2/\text{day}$) were evaluated in the dose-finding portion of part 1 of Study MT103-205. Based on preliminary results of Study MT103-205 in pediatric subjects with ALL, the $5 \mu\text{g}/\text{m}^2/\text{day}$ dose provided blinatumomab mean steady state levels from 150 to 186 pg/mL which

is within a biologically active range (blinatumomab half-maximal concentrations for in vitro target cell lysis: 10 to 100 pg/mL). Patients received between 1 and 5 cycles of blinatumomab. Following Data Review Committee/Data Safety Monitoring Board (DRC/DSMB) review of the safety, efficacy, PK, and PD data from all patients from the phase 1 cohorts, a decision was made to start with a dose lower than the maximum tolerated dose (MTD) (15 μ g/m²/day) for the PK expansion part of phase 1. An initial dose of 5 μ g/m²/day was selected in order to prevent cytokine release syndrome, which was the major toxicity observed. This dosing regimen includes 5 μ g/m²/day for the first week of treatment of the first cycle, increased to 15 μ g/m²/day at the end of the first week of the first cycle. For consolidation, starting from cycle 2, a constant dose of 15 μ g/m²/day is given. With this step dosing the pediatric dosing is comparable to the respective non-BSA based dosing in adult R/R ALL (9 μ g/day, followed by 28 μ g/day)

The effective dose for NHL is expected to be higher than that for the R/R ALL. Based on data from the phase 1 dose-finding Study MT103-104, objective clinical responses were observed starting at 15 μ g/m²/d and peaked at 60 μ g/m²/d. PK/PD analysis suggested the reduction of tumor size was dependent on systemic blinatumomab exposure and treatment duration. Comprehensive analysis is ongoing to further evaluate the optimal doses for the NHL treatment. The dose of 60 μ g/m²/d was established in the NHL phase 1 study as the target dose and was also used in the phase 2 DLBCL study (MT103-208) as the BSA-independent dose of 112 μ g/d.

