5.2 Blinatumomab Administration

Subjects will receive premedication with dexamethasone 20 mg (or equivalent) intravenously 1 hour (+/- 30 minutes) prior to the first dose of blinatumomab of each cycle, prior to a step dose (such as Cycle 1 day 8), or when restarting an infusion after an interruption of 4 or more hours. Blinatumomab will be administered as a continuous IV infusion through a central venous catheter at a constant flow rate using an infusion pump for a 42 day cycle with cycle 1 and a 28 day cycle with cycle 2. Blinatumomab will start with a 7 day infusion at 9mcg/d. If no grade 3 toxicity after 7 days, the dose will be escalated to 28 mcg/d for 7 additional days. If no grade 3 toxicity after 14 days, blinatumomab will be infused at a target dose of at 112mcg/d for 28 days.

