5.4 Criteria for Taking a Participant Off Protocol Therapy

Duration of therapy will depend on individual response, evidence of disease progression and tolerance. In the absence of treatment delays due to adverse event(s), treatment may continue for 2 cycles or until one of the following criteria applies:

- Disease progression
- Intercurrent illness that prevents further administration of treatment
- Unacceptable adverse event(s)
- Participant demonstrates an inability or unwillingness to comply with the oral medication regimen and/or documentation requirements
- Participant decides to withdraw from the protocol therapy
- General or specific changes in the participant's condition render the participant unacceptable for further treatment in the judgment of the treating investigator

Participants will be removed from the protocol therapy when any of these criteria apply. The reason for removal from protocol therapy, and the date the participant was removed, must be documented in the case report form (CRF). Alternative care options will be discussed with the participant.

A QACT Treatment Ended/Off Study Form will be filled out when a participant is removed from protocol therapy. This form can be found on the QACT website or obtained from the QACT registration staff.

In the event of unusual or life-threatening complications, treating investigators must immediately notify the Overall PI, [name] M.D., Ph.D. at [contact].

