6. DOSING DELAYS/DOSE MODIFICATIONS

6.1 Toxicity Management/ Dosage Adjustments

Table 6-1 Criteria for dosing delays and re-initiation of treatment for toxicity definitely or possibly related to study drug. Based on the Common Terminology Criteria for Adverse Events (CTCAE) version 4.0.

Toxicity	Grade	Action
Cytokine Release Syndrome (CRS)	Grade 3	Withhold blinatumomab until resolved to \leq grade 1, then restart blinatumomab at 9 mcg/day with dexamethasone 8mg TID for three days. Dexamethasone will then be decreased by 25% per day until discontinued. Escalate to 28 mcg/day after 7 days and then to 112 mcg/d after an additional 7 days if the toxicity does not recur.
	Grade 4	Remove from study
Neurologic toxicity	Seizure	Discontinue blinatumomab permanently if more than one seizure occurs despite antiepileptics.
	Grade 3	Withhold blinatumomab until \leq grade 1, (mild), then restart blinatumomab at 9 mcg/day with dexamethasone (or equivalent) 20mg iv within 1 hour of start of retreatment. Dexamethasone will then be decreased by 25% per day until discontinued. Escalate to 28 mcg/day after 7 days and then to 112 mcg/d after an additional 7 days if the toxicity does not recur. If the toxicity occurred at 9 mcg/day, or if the toxicity takes more than 7 days to resolve, discontinue blinatumomab permanently
	Grade 4	Remove from study
Other clinically relevant adverse reactions	Grade 3	Withhold blinatumomab until \leq grade 1 (mild), then restart blinatumomab at 9 mcg/day. Escalate to 28 mcg/day after 7 days and then to 112 mcg/d after an additional 7 days if the toxicity does not recur. If the toxicity occurred at 9 mcg/day, or if the toxicity takes more than 7 days to resolve, discontinue blinatumomab permanently
	Grade 4	Remove from study

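### Section 5.1 starts cycle 2 at 112 mcg/d for every non-progressor, with no exception for a subject whose Table 6-1 re-escalation after a late grade 3 hold is incomplete

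*Combined protocol and SAP*

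**What the plan says.** Section 5.1 makes each cycle 1 escalation conditional on no dose-limiting toxicity by Table 6-1. For cycle 2 the only condition is absence of progression: "All subjects without disease progression will receive an additional 4 week cycle starting at the target dose of 112 mcg/d". Section 1.1 gives cycle 2 to the same group without naming a starting dose: "All subjects without disease progression will receive an additional 4 week cycle".

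In Section 6.1, each grade 3 row of Table 6-1 withholds drug until grade 1 or less and restarts at 9 mcg/d. Then: "Escalate to 28 mcg/day after 7 days and then to 112 mcg/d after an additional 7 days if the toxicity does not recur". The neurologic and other-reaction rows stop drug for good if the event occurred at 9 mcg/d, or "if the toxicity takes more than 7 days to resolve, discontinue blinatumomab permanently". The cytokine release row has no such time limit. Grade 4 events remove the subject from study.

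Section 5.2 describes the infusion as "using an infusion pump for a 42 day cycle with cycle 1 and a 28 day cycle with cycle 2". Section 11.1 places the first response scan within 7 days of day 84. Section 5.4 says "treatment may continue for 2 cycles or until one of the following criteria applies"; its criteria include unacceptable adverse events and investigator judgment. They end therapy; they do not provide a lower cycle 2 start. Section 8.1.8 adds no exception.

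**The concern.** Starting cycle 2 directly at 112 mcg/d makes sense for a subject who tolerated 112 mcg/d in cycle 1. It does not fit one who had a grade 3 event at that dose and has not completed the steps that Table 6-1 requires before returning to it. Read as written, Section 5.1 takes that subject back to the causative dose after a 6-week break, with the stepped re-challenge unfinished.

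The dose matters. Section 2.2.5 says that the NHL target of 60 mcg/m2/d "was also used in the phase 2 DLBCL study (MT103-208) as the BSA-independent dose of 112" mcg/d, and Section 2.4.1 links 60 and 90 mcg/m2/d to more severe neurologic events in the NHL studies. Table 2-4 shows grade 3 or higher nervous system events in 22 of 95 NHL patients (23.2%).

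Monitoring is lighter for most of the trial. Section 5.1 admits the first 5 subjects for the first 3 days of cycle 2. After that: "If no grade 4 toxicities are seen, future patients enrolled on study will begin therapy as an outpatient". No section requires admission of later subjects for cycle 2.

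**Working it through.** No stated figure in the plan bears directly on this point, so the check is a day count against the plan's own schedule.

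**1. Schedule.** Cycle 1 is 7 days at 9, 7 at 28 and 28 at 112 mcg/d: 7 + 7 + 28 = 42 days, with 112 mcg/d from day 15. Adding the 6-week break, 42 + 42 = 84, which reproduces the scan day in Section 11.1. The count below assumes that a held subject's cycle 1 infusion also ends on day 42.

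**2. Re-escalation.** Let d be the last infusion day at 112 mcg/d before the hold (15 to 41, so 27 possible days) and h the length of the hold.

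- Restart day: r = d + h + 1
- 9 mcg/d on days r to r+6; 28 mcg/d on days r+7 to r+13; 112 mcg/d from day r+14
- Both lower steps finish by day 42 if r + 13 ≤ 42, that is r ≤ 29
- Restarted but incomplete: r = 30 to 42
- Hold still open on day 42: d + h ≥ 42

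| Hold | Steps completed (r ≤ 29) | Restarted, incomplete (r = 30-42) | Hold open on day 42 |
|---|---|---|---|
| 7 days | d = 15-21 (7) | d = 22-34 (13) | d = 35-41 (7) |
| 3 days | d = 15-25 (11) | d = 26-38 (13) | d = 39-41 (3) |
| 1 day | d = 15-27 (13) | d = 28-40 (13) | d = 41 (1) |

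These are calendar counts, not probabilities. The cytokine release row sets no maximum hold, so its range can be wider.

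**3. Dose reached by day 42.**

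- r = 29: 9 mcg/d on days 29-35 and 28 mcg/d on days 36-42. Both steps are complete, so this subject is not affected.
- r = 30 to 35: 36 − r days at 28 mcg/d, so 6 down to 1 instead of 7. The next dose is 112/28 = 4 times the last one.
- r = 36 to 42: 9 mcg/d only, for 43 − r = 7 down to 1 days. The next dose is 112/9 = 12.4 times the last one.
- Hold open: no re-challenge in cycle 1.

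**4. Events at 28 mcg/d.** These start no later than day 14. With a hold of up to 7 days, r ≤ 14 + 7 + 1 = 22, so re-escalation finishes in time. The gap mainly concerns events at 112 mcg/d.

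**5. Recurrence.** If a first event at 112 mcg/d (d ≥ 15) is held at least 1 day, r ≥ 17 and 112 mcg/d returns on day 31 or later. If the event recurs at 112 mcg/d, a second hold of at least 1 day gives a restart on day 33 or later, or none in cycle 1. Such a subject, if kept on drug, always falls in the gap.

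**6. Frequency.** Table 2-2 gives 23 of 95 NHL patients (24.2%) with an adverse event leading to interruption; 0.242 × 28 = 6.8 subjects for any interruption at any time. The share occurring late in cycle 1 is not given. Section 2.4.1 puts most neurologic events in week 1, and Section 7.1.2 gives a median onset of 7 days, so the affected number is well below 6.8.

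**The case against.** The strongest reply is that the words of Section 5.1 cannot be literal. Table 6-1 already takes off drug some subjects who have not progressed, so Section 5.1 must be read subject to it, and the table's restart rule is not limited to cycle 1. A reader might infer that the plan plainly sends a subject with an open hold straight to 112 mcg/d. The documents do not support that: the next infusion for this subject is a re-initiation after toxicity, and a site could reasonably start at 9 mcg/d. What stands there is an unresolved conflict. The reply does not help a subject who has already restarted in cycle 1, because Section 5.1 alone then sets the cycle 2 dose.

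Second, the day-42 end is an assumption. The sections giving 42 days describe an uninterrupted course, and restaging is tied to a 6-week break after the infusion. If held days pushed the schedule back, re-escalation could finish within cycle 1. This stands as a limit, but no section says that missed days are made up, and the fixed day-84 scan points the other way.

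Third, the 4-fold step is not abnormal in itself. It is the 28-to-112 step planned for every subject; the deviation is a 28 mcg/d period shorter than 7 days. Only restarts on days 36 to 42 skip that level.

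Fourth, a reader might infer that 28 − 5 = 23 subjects are exposed without inpatient monitoring. That is the number outside the admission rule, not the number at risk. Table 6-1 also requires no admission for any re-challenge.

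Finally, investigators may stop therapy under Section 5.4, dexamethasone precedes each cycle (Section 5.2), and cytokine elevation is seen in fewer patients and is much less intense in later cycles (Section 2.2.4). These reduce the risk. They do not supply a lower starting dose, and Section 2.2.4 does not address neurologic toxicity.

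**Conclusion.** The point holds as a gap in the dosing rule, and the sponsor should close it. Assuming that cycle 1 ends on day 42 without make-up days, a subject restarted on days 30 to 42 goes to 112 mcg/d in cycle 2 without completing the Table 6-1 step-up. A hold open on day 42 leaves two rules giving 9 and 112 mcg/d for the same infusion.

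The number affected is probably a few subjects; the documents do not allow a firmer estimate. The issue is safety only: the dosing rule does not enter the two-stage calculation in Section 13.2, so no error rate or sample size changes. Confidence is medium, because the end of cycle 1 after a hold is not stated.

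**What to change.** Add to Section 5.1, with a cross-reference in Table 6-1: *A subject held for grade 3 toxicity in cycle 1 who remains eligible for treatment but has not completed the Table 6-1 re-escalation without recurrence by the end of cycle 1 starts cycle 2 at 9 mcg/d for 7 days, then 28 mcg/d for 7 days, then 112 mcg/d only if the toxicity does not recur.*

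Also state when cycle 1 ends after a hold, and conform the cycle 2 length in Sections 1.1, 5.1 and 5.2: up to 42 days for these subjects, with the end-of-treatment scan 6 weeks after the infusion ends.

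Cost per affected subject:

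- Infusion: up to 14 more days (42 versus 28).
- Drug: 7×9 + 7×28 + 28×112 = 3,395 mcg, against 28×112 = 3,136 mcg, so 259 mcg more.
- Two more dexamethasone step doses under Section 5.2.
- No extra subjects or scans. With cycle 2 starting at about day 84, the end-of-treatment scan falls at about 84 + 42 + 42 = day 168, the day named in Section 11.1.

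Keeping the stepped cycle 2 to 28 days would avoid the extra infusion time but deliver only 7×9 + 7×28 + 14×112 = 1,827 mcg, 58% of the planned amount. The longer cycle is preferable.
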